Clinical photographs will be obtained with the same digital camera (Nikon D5100 DSLR) mounted on a ring flashlight, using the same lens (Sigma Macro 105mm F2.8 EX) and the same focal length. The photographs are taken under the same lightning conditions and camera settings. The patients are sitting in an upright position, looking straight ahead. The Frankfort plane of the patient as well as the camera lens is positioned parallel to the ground. The photographs will be captured perpendicular to the teeth adjacent to the deficient papilla. Strict care is taken to ensure that the same up-down and right-left shooting positions are reproduced at different time intervals.

- -The surface area of the black triangle (SABT) is assessed using standardized digital clinical photographs analyzed by an image analysis program (Photoshop Cs 5, Adobe Systems, San Jose, CA, USA). The surface area of the black triangle was assessed from the photographs taken at baseline (before injection), 3 and 6 months from the first injection.
- 10 mm William's graduated periodontal probe was used as a scale for calibration.

Papilla Presence Index (PPI): (Cardaropoli etal. 2004)

- -PPI (1): is reported when papilla is completely present and coronally extends to the contact point to completely fill the inter-proximal embrasure which this papilla is at the same level as the adjacent papillae.
- -PPI (2): describes a papilla that is no longer completely present and lies apical to the contact point which this papilla is not at the same level as the adjacent papillae and the embrasure is no longer completely filled but the interproximal cemento-enamel junction is still not visible.
- -PPI (3): refers to the situation in which the papilla is moved more apical and the cemento-enamel junction becomes visible.
- -PPI (4): describes when the papilla lies apical to both the incisal cemento-enamel junction and buccal cemento-enamel junction which interproximal soft tissue recession is present together with buccal gingival recession and patients esthetics is dramatically compromised.

Clinical attachment level (CAL):

CAL will be determined by measuring the distance from the cemento-enamel junction to the base of the pocket using a UNC 15 periodontal probe.

Probing depth (PD):

Probing depth will be measured from the gingival margin to the base of the periodontal pocket using a UNC 15 periodontal probe.

Gingival recession (GR):

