This power analysis used interdental papilla loss after six months as the primary outcome. Based upon the results of Awartani FA and Tatakis DN (2016), the mean and standard deviation (SD) for control group were 0.71 (0.74) mm2. The minimal clinically significant difference was 1 mm2according to expert opinion. Using alpha (α) level of (5%), β level of 0.8 (Power = 80%); the effect size for independent samples t-test (d) was 1.32 and the minimum estimated sample size was 10 sites per group. Sample size was increased to 12 sites per group to compensate for a drop-out rate of 20% after six months. Sample size calculation was performed using PS Power and Sample Size Calculations Version 3.

15. Recruitment strategy

- The main investigator will be responsible for recruitment of patients.
- Patients will be selected from the outpatient clinic of the Oral Medicine and Periodontology
 Department, Faculty of Dentistry Cairo University.
- Screening of patients will continue until the target sample is achieved.
- Identifying and recruiting potential subjects will be achieved through patient database.
- 1. One year.
- 2. Candidate self-funding

B) Assignment of interventions

16. Allocation

16a. Randomization

The patients will be randomly allocated to either the intervention group or the control group using computer generated random numbers that will be performed by the supervisor. The patients will be allocated in a ratio of 1:1.

16b. Allocation concealment mechanism

The two groups will be equally prepared for both surgical procedures. Then the decision of which group will receive Hyaluronic acid injection and which will Tube Technique will be taken according to the randomized numbers placed in opaque sealed envelopes. The number will be picked by the supervisor.

16c. Implementation

The supervisor will be responsible for generation of allocation sequence as will as assign the patients to the 2 intervention groups. The main investigator will be responsible for patient enrollment.

17. Masking/blinding:

Due to the type of intervention only the outcome assessor and the statistician will be blinded. Single blinded:

- Blinding of the participants is not applicable.
- Blinding of the operator is not applicable.
- Outcome assessor (primary and secondary outcomes) and biostatistician will be blinded.

Key elements of Random Sequence Generation in protocol are:

- 1-Method of random sequence generation (computerized random number generator).

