- 2- Allocation ratio (1:1, 2:1).
- 3- Type of randomization: simple, blocked, stratified.

c) Data collection, management, and analysis:

18. Data collection methods

- All the data of the patients included in the study will be recorded from them or extracted from the patient's periodontal chart.

- Telephone numbers of all patients included in the study will be recorded as a part of the written consent.
- All patients will receive a phone call at the time of the pre-determined follow up dates.

19. Data management:

Excel sheet program will be used though a computer system to manage the data with a secured password.

20. Statistical methods:

- The outcome used (State 1ry or 2ry): interdental papilla loss area (mm2)
- Values used for outcome (e.g. mean difference, percentage, proportion..... etc): mean and standard deviation
- Entry 1: (mean difference between 2 groups, mean and standard deviation of group 1, proportion 1 or estimated prevalence):

Minimal clinically significant difference = 1 mm2 according to expert opinion

• Entry 2: (standard deviation of control group, mean and standard deviation of group 2, proportion 2 or clinically important difference):

Mean of the control group = 0.71

SD of control group = 0.74

- Alpha level of significance: 0.05
- Effect size used in calculation: d = 1.32
- Power of the study: 0.8
- Statistical test used: Independent samples t-test
- The calculated sample size: 10 sites per group.
- Increased number for anticipated missing data: Sample size will be increased to 12 sites per group to compensate for a drop-out rate of 20% after six months.

D) Data monitoring:

21. Monitoring

No formal data monitoring committee will be needed since it is a study with known minimal risks.

22. Harms

Postoperative pain and/or swelling will be managed through analgesics.

23. Audit

Auditing of the study design will be done by the evidence-based committee – Faculty

Dentistry – Cairo University.

IV. Ethics and dissemination

24. Research ethics approval

This protocol and the template informed consent form will be reviewed by the Ethics Committee of Scientific Research -Faculty of Dentistry- Cairo University.

25. Protocol amendments

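### The only test named for the six-month black-triangle area ignores the scheduled 3-month reading; the sample-size inflation largely covers the expected 20% loss in power but not the bias if loss is selective

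*Protocol*

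**What the plan says.** - **Primary outcome and time.** Protocol section 14 (Sample size): "This power analysis used interdental papilla loss after six months as the primary outcome". The outcome table in section 12 identifies this as the black-triangle area (SABT), read from photographs.
- **Test.** Section 20 (Statistical methods) lists the outcome, the sample-size inputs and one test: "Statistical test used: Independent samples t-test". The neighbouring entries are "Alpha level of significance: 0.05", "Power of the study: 0.8", "Minimal clinically significant difference = 1 mm2 according to expert opinion" and "SD of control group = 0.74".
- **Missing data.** Sections 14 and 20 raise the calculated 10 sites per group to 12 to "compensate for a drop-out rate of 20% after six months". Nothing else is said about sites without a six-month value.
- **Photographs.** Section 12 says SABT is assessed from "photographs taken at baseline (before injection), 3 and 6 months from the first injection". The 3-month area is therefore scheduled, but it has no stated role in the primary comparison.
- **Blinding and burden.** Section 17 says participants cannot be blinded. Section 11 describes surgery with a harvested graft in one arm and three injections over six weeks in the other.

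**The concern.** A two-sample t-test on six-month area takes one number per site, so a site without that number contributes nothing, even if its area was measured at three months. Enrolling more sites replaces the lost count. It does not make those who stay representative of those who started.

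Selective loss is plausible here. Patients know their arm, the two treatments burden them differently, and the result is cosmetic and visible to the patient by month 3. If poor early responders leave one arm more than the other, the completers' difference is shifted. If the poor responders leave the control arm, the advantage of the surgical technique is understated; if they leave the surgical arm, it is overstated by the same amount. The 3-month photograph is the information needed to correct this, and the protocol already collects it.

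**Working it through.** **Inputs from the protocol:** difference 1 mm2, SD 0.74, stated d = 1.32, alpha 0.05, power 0.80, ratio 1:1, 10 sites per group raised to 12, 20% loss.

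**Assumptions, not in the protocol:** two-sided alpha (it reproduces the stated n; one-sided gives about 8); correlation rho between the 3- and 6-month areas; when drop-out happens; who drops out.

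**1. The plan's own figure.** A two-sided t-test at d = 1.32 needs 10.07 per group (10 by the normal approximation). The stated 10 is reproduced. The stated inputs give d = 1/0.74 = 1.35, which needs 9.66, so the mismatch is immaterial here.

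**2. Power after the expected loss.** Completers per group: 12 × 0.8 = 9.6.
- d = 1.32: power 77.9%.
- d = 1.35: power 79.7%.

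Inflation therefore nearly holds the 80% target. The small gap at d = 1.32 arises because 10 × 1.2 = 12 was used, whereas 10/0.8 = 12.5, that is 13.

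**3. Power gain from the 3-month reading under random loss.** With n_obs completers and m drop-outs who have a 3-month value, the large-sample effective size per arm is

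n_eff = n_obs / (1 − rho² × m/(n_obs + m)).

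For 12 per group with every drop-out seen at month 3 (m = 2.4) and rho = 0.5: 9.6/(1 − 0.25 × 0.2) = 10.11. Power at d = 1.32:

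| Setting | No 3-month data | rho 0.5 | rho 0.7 | rho 0.8 | rho 0.9 |
|---|---|---|---|---|---|
| 12 per group, all drop-outs seen at month 3 | 77.9% | 80.2% | 82.4% | 83.8% | 85.3% |
| 12 per group, half seen at month 3 | 77.9% | 79.1% | 80.4% | 81.2% | 82.0% |
| 18 per group, all seen at month 3 | 92.7% | 93.9% | 95.0% | 95.7% | 96.3% |

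The last row is shown because section 11 of the protocol gives 18 sites per group, in conflict with the 12 in sections 14 and 20. These figures are slightly optimistic, since they ignore the cost of estimating the covariance in a small sample. With small-sample inference, simulation at 12 per group gives about 79% rising to 80–85% at SD 0.74, and about 78% rising to 79–84% at d = 1.32. The gain is about 0 to 7 points.

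**4. Bias under selective loss.** Scenario: 12 per group, SD 0.74, true difference 1 mm2. The 20% with the poorest 3-month response leave the control arm, and a random 20% leave the other arm.

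Large-sample check: removing the lowest fifth of a normal distribution raises the mean of the rest by 0.280/0.8 = 0.35 SD (0.280 is the normal density at the 20th percentile). The six-month mean moves by rho × 0.35 × 0.74:
- rho = 0.5: 0.13 mm2.
- rho = 0.8: 0.21 mm2.

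Simulation at 12 per group gives slightly smaller shifts:

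| rho | t-test estimate | Shift | t-test power | t-test type I error, no true difference | Likelihood estimate |
|---|---|---|---|---|---|
| 0.5 | 0.88 | 0.12 | 71% | about 7% | 1.00 |
| 0.8 | 0.81 | 0.19 | 66% | about 10% | 1.00 |

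The bias depends on the fraction lost, not on the number enrolled, so more sites do not reduce it.

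**The case against.** **The quoted line is a sample-size entry, not an analysis rule.** It does sit in a filled-in sample-size form. A reader might infer that the protocol orders sites without a six-month value to be dropped. It does not: it states no analysis set, exclusion rule or complete-case rule. What stands is narrower. The form is the whole of the section headed Statistical methods, it names a single test, and that test can use only sites with a six-month value.

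**Missing-data handling belongs in the statistical analysis plan, which is not shown.** This is right for a missing rule, and its absence is not criticised here. The point is that the method the protocol does name makes no use of a primary-outcome reading it has scheduled, while 20% loss is forecast.

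**The loss of power is already paid for.** This largely stands. A reader might infer a serious power deficit from the expected loss, but at 78 to 80% after 20% loss the plan is close to target. The further gain is modest, and it shrinks if sites are lost before month 3 or if 18 per group are enrolled.

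**The bias is hypothetical.** This also stands. The scenario is one-sided by construction, and the documents contain no evidence of such drop-out. In addition, if patients leave for reasons that the recorded areas do not reflect, such as unrecorded discomfort, the likelihood model is biased too.

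**A t-test at one fixed time point is legitimate in a small trial.** It is. The proposal is an improvement at little cost, not the correction of an error that invalidates the trial.

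**Conclusion.** The concern holds in limited form, as a desirable improvement rather than an essential one. The named t-test cannot use the 3-month areas of sites lost before month 6, and the inflation from 10 to 12 sites protects power but not against selective loss. In the one-sided scenario the estimate is off by 0.12 to 0.19 mm2, or 12 to 19% of the 1 mm2 target, and the type I error rises to about 7 to 10%. The likelihood estimate stays at 1.00 mm2.

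These sizes rest on an assumed correlation of 0.5 to 0.8, on loss occurring after month 3, and on drop-out that depends on the 3-month reading in one arm only. The case for change rests on bias; the power gain of about 0 to 7 points is secondary.

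**What to change.** In section 20, make the primary analysis a likelihood-based repeated-measures model of SABT using the 3- and 6-month readings, with arm, time and arm-by-time terms, an unstructured covariance and Kenward-Roger degrees of freedom. State that the six-month contrast between arms is the primary estimate, and keep the independent samples t-test as a supporting analysis. Reconcile 12 and 18 sites per group, since the power figures depend on which applies.

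**Cost:** analysis wording and some programming, with no added visits, patients or measurements. **Downside:** at this size the model needs the small-sample correction, and its protection holds only if drop-out depends on readings that were observed. Sites lost before the 3-month photograph gain nothing from it.

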It is a minimally invasive non-surgical injection of hyaluronic acid that observed to overcome the major limiting factor in most surgical techniques regarding the limited blood supply and the small working space. Supported by a recent study conducted by *Jinng etal.* 2019, who reported significant increase in the height of the gingival papilla and reduction of the area of the black triangle between baseline and 3 or 6 months in a group with thick gingival biotype after injection with hyaluronic acid, that was adding possible maximum effect with minimal postoperative hazards.

II.B. Objectives of the study:

7. Aim of the study

The aim of this randomized clinical trial is to compare the clinical effect of surgical Tube technique versus Hyaluronic Acid gel injection in reconstruction of the interproximal papilla in patients with class II papillary defect.

Picots:

P: Population: patients with class II papillary defect.

I: Intervention: Tube technique hosting sub-epithelial connective tissue graft.

C: Control: Hyaluronic acid injection.

Primary outcome: interdental papilla loss (Decrease of black triangle) (mm2)

Secondary outcome: assessment of gain in papillary height, radiographic distance between (CP-

BC), assessment of CAL. PD reduction, amount of gingival recession.

T: Time frame: 6 months.

S: Study design: Randomized clinical trial.

Hypothesis:

Null hypothesis: There is no difference in the gain in papillary height comparing hyaluronic acid injection versus Tube technique in patients with class II papillary defect.

8.Trial design

The study is designed as a superiority, 2 arm parallel groups, randomized clinical trial with allocation ratio 1:1.

III. Methods

A) Participants, interventions and outcomes

9. Study settings:

This study will be carried out on patients enrolled from the outpatient and postgraduate clinics of Oral Medicine and Periodontology department, Faculty of Dentistry, Cairo University.

10. Eligibility criteria:

Inclusion Criteria:

- Highly motivated patients with papillary deficiency types II, according to *Nordland* and *Tarnow 1998* classification will be selected, having at least one deficient papilla in the anterior region.
- Distance between the contact point and inter-proximal bone crest (CP-BC) of ≤ 7 mm and probing depth of ≤ 4 mm at the deficient papillary site (*Abdelraouf etal. 2019*).
 - Patients with full mouth plaque index (PI) and gingival index (GI) scores should be between 0-1.

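### The only test named for black-triangle area is an unadjusted t-test, although baseline area is measured; adjusting for it would improve precision and remove chance baseline imbalance at almost no cost

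*Protocol*

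**What the plan says.** Section 20 (Statistical methods) identifies the outcome as papilla loss area in mm² and gives the method as "Statistical test used: Independent samples t-test". The line stands in a list with "Alpha level of significance: 0.05", "Power of the study: 0.8", "Minimal clinically significant difference = 1 mm2 according to expert opinion", a control mean of 0.71, an SD of 0.74, an effect size of 1.32 and 10 sites per group, raised to 12 for dropout. Section 14 (Sample size) had already given the same calculation.

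Section 12 (Outcomes) says that the surface area of the black triangle (SABT) is "assessed from the photographs taken at baseline (before injection), 3 and 6 months from the first injection". This timing is worded around the injection arm. I read it as covering both arms, because SABT is the primary outcome and section 11 has clinical parameters recorded at baseline before the two groups are described.

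The outcome itself is worded in two ways. The PICOTS list in section 7 has "Primary outcome: interdental papilla loss (Decrease of black triangle) (mm2", a change from baseline, and the section 12 table agrees. Section 14 says "This power analysis used interdental papilla loss after six months as the primary outcome", which reads as a final value.

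Section 11 gives 36 sites, 18 per group, which differs from the 12 per group in sections 14 and 20. No covariate and no stratification by baseline area is specified anywhere.

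**The concern.** The size of the triangle at the start is likely to predict its size at 6 months. In a trial this small the two groups can easily start with different mean areas by chance. A two-sample t-test on the final value ignores this information. A t-test on the change uses it only by subtraction, which over-corrects whenever r is below 1 and the variances are similar. Either way the confidence interval is wider than it needs to be at moderate r, and part of any chance imbalance stays in the treatment difference. The covariate that would deal with both is already being collected.

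**Working it through.** **Inputs.** From sections 14 and 20: difference 1 mm², SD 0.74, d = 1.32, alpha 0.05 (taken as two-sided), n = 10 per group, 12 after dropout. From section 11: 18 per group. Assumed, because the documents do not give them: r between baseline and 6-month area of 0.3, 0.5 or 0.7, and equal baseline and 6-month variances.

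**1. The plan's own figure.** Noncentral-t power with noncentrality d × √(n/2) and 2n − 2 degrees of freedom. At n = 10, the stated d = 1.32 gives 79.7%, and d = 1/0.74 = 1.351 gives 81.5%. The stated 10 per group is reproduced within rounding.

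**2. ANCOVA, by what the SD of 0.74 refers to.** Degrees of freedom 2n − 3, d = 1/(residual SD).

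- If 0.74 is the SD of the 6-month value, the residual SD is 0.74 × √(1 − r²).
- If 0.74 is the SD of the change, its variance is 2σ²(1 − r) and the ANCOVA residual variance is σ²(1 − r²). The ratio is (1 + r)/2, so the residual SD is 0.74 × √((1 + r)/2).

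Power at 10 per group, against 81.5% for the t-test on the same inputs:

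| r | Residual SD (final value) | Power | Residual SD (change) | Power |
|---|---|---|---|---|
| 0.3 | 0.706 | 84.7% | 0.597 | 94.2% |
| 0.5 | 0.641 | 90.8% | 0.641 | 90.8% |
| 0.7 | 0.528 | 97.8% | 0.682 | 87.0% |

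The gain is present under both readings, but it rises with r under one and falls under the other.

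**3. Check by simulation.** The formula leaves out the variance added by chance imbalance in the covariate. Simulated normal data with the same inputs (20,000 runs each) give about 83%, 89% and 97% for the final-value reading and 93%, 89% and 85% for the change reading. The table is therefore about 1–2 points high. At r = 0 on the final-value reading, ANCOVA loses about 2–3 points (79% against 81.5% here; 77% against 80% in a simulation at d = 1.32).

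**4. At 18 per group.** The t-test has 97.0% (d = 1.32) to 97.6% (d = 1.351). ANCOVA gives between 98.1% and just under 100% across both readings, a gain of about 1–3 points.

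**5. Chance imbalance.** The standard error of the baseline difference is √(2/n) baseline SDs: 0.45, 0.41 and 0.33 at 10, 12 and 18 per group. The chance of an imbalance above 0.5 SD is 26%, 22% and 13%. Shift in the unadjusted estimate for a one-standard-error imbalance at 12 per group (0.408 SD):

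- Final value, baseline SD taken as 0.74: r × 0.74 × 0.408 = 0.09, 0.15, 0.21 mm² for r = 0.3, 0.5, 0.7.
- Change (6 months minus baseline), baseline SD = 0.74/√(2(1 − r)) = 0.625, 0.740, 0.955: (r − 1) × SD × 0.408 = −0.18, −0.15, −0.12 mm².

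**6. Which reading fits the figures.** With a control mean of 0.71 and a 1 mm² benefit for the tube technique, a final-value reading implies 0.71 − 1 = −0.29 mm², which is impossible for an area. Read as decreases, 0.71 and 1.71 are possible. This favours the change reading but does not settle it, since section 14 says otherwise.

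**The case against.** The strongest objection is that the t-test line is a sample-size entry. It sits between power and the calculated n, and no sentence says how the 6-month data will be analysed, so the model may be set in an analysis plan that is not shown. This stands in part. But section 14 already covers the sample size, and section 20 is the only statistical-methods section. A reader has no other primary comparison to take from the protocol.

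The second objection is that a t-test on the decrease in area already uses baseline. That is correct if the change is what is tested. Subtraction is still less efficient than ANCOVA under equal variances for any r below 1, as the (1 + r)/2 ratio shows.

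Three stronger readings are tempting and are not supported:

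- That the t-test is wrong or underpowered. It is unbiased over randomization, its simulated type I error is about 5%, and the stated n roughly reproduces.
- That a baseline imbalance passes in full into the estimate. It enters multiplied by r or by (r − 1).
- That the power gain is known and grows with r up to 98%. That holds only if 0.74 is the SD of the final value, which the outcome wording and the control mean make doubtful.

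**Conclusion.** The point holds as a recommendation on efficiency and robustness, worth making but not a correction of an error. At 10 per group, ANCOVA would add roughly 3–16 points of power by formula if 0.74 is the SD of the 6-month value, or 5–13 points if it is the SD of the change, for r between 0.3 and 0.7. Simulation puts each gain slightly lower. It would also remove a shift of about 0.1–0.2 mm² for a typical chance imbalance at 12 per group, set against a target difference of 1 mm². At 18 per group the power argument nearly disappears and the imbalance argument remains, in weaker form. All of this rests on an assumed r, on equal variances, and on a two-sided 5% test.

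**What to change.** State in section 20 that the primary analysis is a linear model (ANCOVA) of 6-month SABT on treatment group with baseline SABT as covariate, reporting the adjusted difference with its 95% CI. Say there that the t-test is the basis of the sample size only.

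With baseline in the model, the treatment effect (apart from sign) and its P value are the same whether 6-month area or change is the response, so the two wordings of the outcome no longer affect the test. The outcome definition should still be worded one way throughout.

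The cost is one sentence, no new data and one degree of freedom, with a loss of up to about 2–3 points of power at 10 per group if baseline turns out uninformative (r near 0 for a final-value outcome). The change should be made before any unblinded outcome data are seen.
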